8.4 Adverse Events and Serious Adverse Events

8.4.1 Definitions

8.4.1.1 Adverse event

An AE is any untoward medical occurrence in a clinical study patient administered a pharmaceutical product and which does not necessarily have a causal relationship with this treatment. An AE can therefore be any unfavorable and unintended sign (including clinically significant abnormal values from relevant tests, such as clinical safety laboratory tests, ECGs, vital signs), symptom, or disease temporally associated with the use of an IMP, regardless of whether it is considered related to the IMP.

A TEAE is any AE only present after the initiation of IMP administration or any event already present that worsens in either intensity or frequency following exposure to the IMP.

Collection of AEs will start directly after the ICF has been signed. Only AEs related to study procedure will be collected between screening visit and the first IMP administration.

8.4.1.2 Serious adverse event

An SAE is any AE that:

- results in death
- is life-threatening (this refers to an event in which the patient was at immediate risk of death at the time of the event; it does not refer to an event that hypothetically might have caused death if it had been more severe)
- requires inpatient hospitalization or prolongation of existing hospitalization
- results in persistent or significant disability/incapacity
- is a congenital anomaly/birth defect
- is medically important (this refers to an event that may not be immediately life-threatening or result in death or hospitalization, but may jeopardize the patient or may require intervention to prevent any of the SAEs defined above)

Examples of medically important events are intensive treatment in an emergency room for allergic bronchospasm or blood dyscrasias, convulsions that do not result in hospitalization, development of drug dependency, and drug abuse.

Hospitalization is defined as any inpatient admission usually involving at least an overnight stay.

Planned hospitalizations or surgical interventions for a condition that existed before the patient signed the ICF and that did not change in intensity are not SAEs.

If there is any doubt as to whether an AE meets the definition of an SAE, a conservative viewpoint must be taken, and the AE must be reported as an SAE.

8.4.1.3 Adverse events of special interest (AESI)

An AESI (serious or non-serious) is one of scientific and medical concern specific to the Sponsor's product or program, for which ongoing monitoring and rapid communication by the Investigator to the Sponsor can be appropriate. Such an event might warrant further investigation in order to characterize and understand it.

All AESI, serious and non-serious, **must be reported within 24 hours** of identification using the same reporting process as for SAE reporting.

The following conditions should be considered AEs of special interest and require expedited reporting:

- a. ALT or AST $\geq 8 \times$ ULN
- b. ALT or AST $\geq 5 \times$ ULN for 2 or more weeks
- c. ALT or AST $\geq 3 \times$ ULN **and** total bilirubin $\geq 2 \times$ ULN (or ALT or AST $\geq 3 \times$ ULN **and** INR > 1.5)
- d. ALT or AST $\geq 3 \times$ ULN accompanied by clinical symptoms believed to be related to hepatitis or hypersensitivity, such as new or worsening of fatigue, nausea, vomiting, right upper quadrant pain or tenderness, fever, or rash
- e. ALT or AST $\geq 5 \times$ ULN but $< 8 \times$ ULN and cannot be monitored at least weekly for ≥ 2 weeks

Hy's Law, defined as $\geq 3 \times$ ULN ALT or AST **with coexisting** $\geq 2 \times$ ULN total bilirubin with no alternative explanation for the biochemical abnormality other than IMP (for example elevated ALP indicating cholestasis, viral hepatitis, other medication) must always be reported without delay as an AESI, and, if applicable, also as an SAE.

All potential drug-induced liver injuries (PDILI) events require immediate action, testing, and monitoring. If tests are done locally for more rapid results, a concurrent sample should also be sent to the central laboratory whenever possible.

PDILI events require notification of the Medical Monitor within 24 hours (e.g., by laboratory alert), and the patient must be discussed with the Medical Monitor as soon as possible. Patients with PDILI must be assessed to determine if the study drug must be discontinued (please refer to General withdrawal criteria, Section 7.1).

To ensure patient safety and enhance reliability in determining the hepatotoxic potential of an investigational drug, a standardized process for identification, monitoring and evaluation of liver events has to be followed.

Every liver laboratory trigger or liver event as defined in Table 2 should be followed up by the Investigator or designated personnel at the trial site as summarized below (please also refer to General withdrawal criteria, Section 7.1).

A. Liver laboratory trigger:

- Repeating the LFT within the next week to confirm elevation. The repeat assessment can be done as an unscheduled study visit or at a local laboratory. In this case, local laboratory normal ranges should be recorded, and the results should be made available to the trial investigator immediately, and the data recorded on the CRF.
- If the elevation is confirmed, close observation of the patient will be initiated, including consideration of treatment interruption if deemed appropriate.

B. Liver event:

- Repeating the LFT as soon as possible to confirm elevation as appropriate
- Monitoring of liver chemistry values at least twice per week until values normalize, stabilize, or return to within baseline value
- Discontinuation of the investigational drug if appropriate
- Hospitalization of the patient if appropriate
- A causality assessment of the liver event via exclusion of alternative causes (e.g., disease, co-medications)
- An investigation of the liver event which needs to be followed until resolution.

These investigations can include serology tests, imaging and pathology assessments, hepatologist's consultancy, based on investigator's discretion. All follow-up information, and the procedures performed should be recorded on appropriate CRF pages, including the liver event overview CRF pages.

Table 2 Liver Event and Laboratory Trigger Definitions

	Definition/ threshold
A. LIVER LABORATORY TRIGGERS	ALT or AST > 3 × ULN, but ALT and AST ≤ 5 × ULN TBL > 1.5 × ULN, but TBL ≤ 2 × ULN
B. LIVER EVENTS	
Laboratory events (any of the listed criteria)	ALT or AST > 5 × ULN ALP > 5 × ULN TBL > 2 × ULN (in the absence of known Gilbert syndrome) Potential Hy's Law cases (defined as ALT or AST > 3 × ULN and TBL > 2 × ULN [mainly conjugated fraction] without notable increase in ALP to > 2 × ULN)
Adverse events (any of the listed criteria)	Any clinical event of jaundice (or equivalent term) ALT or AST > 3 × ULN accompanied by (general) malaise, fatigue, abdominal pain, nausea, or vomiting, or rash with eosinophilia Any adverse event potentially indicative of a liver toxicity *

*These events cover the following: hepatic failure, fibrosis and cirrhosis, and other liver damage-related conditions; the non-infectious hepatitis; the benign, malignant and unspecified liver neoplasms

It is the responsibility of the Investigator to follow up on all SAEs until the patient has recovered, stabilized, or recovered with sequelae, and to report to the Sponsor or Designee all relevant new information using the same procedures and timelines as those for the initial report. Relevant information includes discharge summaries, autopsy reports, and medical consultation.

Serious adverse events spontaneously reported by a patient to the Investigator within 30 days after the last follow-up assessment must be handled in the same manner as SAEs occurring during the study. These SAEs will be reported to the Sponsor or Designee.

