7.1 General Withdrawal Criteria

Patients are free to discontinue their participation in the study at any time and for whatever reason without affecting their right to an appropriate follow-up investigation or their future care. If possible, the reason for withdrawal of consent should be documented.

Patients may be discontinued from the study at any time at the discretion of the Investigator for any of the following reasons:

- Severe non-compliance to study protocol procedures, as judged by the Investigator and/or Sponsor

- Significant AEs posing a risk for the patient, as judged by the Investigator and/or Sponsor
- Withdrawal of informed consent by the patient. If consent is withdrawn, the patient will not receive any further study treatment or further study observation. Note that the patient may need to undergo additional tests to withdraw safely
- Withdrawal of informed consent by the patient to the use of biological samples as judged by the Investigator and/or Sponsor
- At the discretion of the Investigator, when he/she believes continued participation is not in the best interest of the patient
- Positive pregnancy test (Pregnant women should be followed until delivery as described in Section 8.4.8)
- Severe laboratory abnormalities (please refer to Treatment and follow-up of AEs in Section 8.4.7):
 - Alanine aminotransferase (ALT) or aspartate aminotransferase (AST) $> 8 \times$ upper limit of normal (ULN)
 - AST or ALT $> 5 \times$ ULN (for more than 2 weeks)
 - ALT or AST $> 3 \times$ ULN with total bilirubin (TBL) $> 2 \times$ ULN (unless elevated bilirubin is related to confirmed Gilbert's Syndrome) or with international normalized ratio (INR) > 1.5
 - ALT or AST $> 3 \times$ ULN with the appearance of fatigue, nausea, vomiting, right upper quadrant pain or tenderness, fever, rash, and/or eosinophilia ($> 5\%$)
- Diagnosis of a malignancy during study (excluding carcinoma in situ of the cervix, or squamous or basal cell carcinoma of the skin).
- The Sponsor or a Regulatory Agency requests withdrawal of the patient.

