8.4.7 Treatment and Follow-up of Adverse Events

Patients with AEs that occur during the study must be treated according to daily clinical practice at the discretion of the Investigator. Adverse events must be followed up until resolution or until End of Study/Early Termination visit, whichever comes first. At the follow-up visit, information on new AEs, if any, and stop dates for previously reported AEs must be recorded. Adverse events assessed as stable by the Investigator at the End of Study/Early Termination visit will not have to be followed up until resolution.

For the treatment and follow-up of AESIs please refer to Section 8.4.1.3.

All SAEs not resolved by the end of the study or that have not resolved upon the patient's discontinuation in the study must be followed until the event resolves, the event stabilizes, or the event returns to baseline if a baseline value is available.

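### Table 2 of the liver follow-up rules has no INR criterion, so an isolated ALT or AST above 3 and up to 5 × ULN with INR above 1.5 meets only the lighter follow-up tier by its terms

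*Protocol*

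**What the plan says.** Three parts of the protocol deal with ALT or AST above 3 × ULN together with INR above 1.5.

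- **Table 2 and its follow-up steps (8.4.1.3).** Row A covers ALT or AST above 3 but not above 5 × ULN. The first step is "Repeating the LFT within the next week to confirm elevation". The next is "If the elevation is confirmed, close observation of the patient will be initiated, including consideration of treatment interruption if deemed appropriate". Row B is stricter. It wants the repeat as soon as possible, liver chemistry at least twice weekly until values settle, a causality work-up that excludes other causes, and investigation until resolution. No criterion in either row mentions INR.
- **AESI list (8.4.1.3, item c).** ALT or AST of at least 3 × ULN with INR above 1.5 is an AESI with no further condition, to be reported within 24 hours. SAP 4.11.2 repeats the item.
- **Withdrawal criteria (7.1).** Under severe laboratory abnormalities, ALT or AST above 3 × ULN counts when it occurs with TBL above 2 × ULN "or with international normalized ratio (INR) > 1.5". The list is discretionary: "Patients may be discontinued from the study at any time at the discretion of the Investigator for any of the following reasons".

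The cross-references run in a circle. For severe laboratory abnormalities, 7.1 says "please refer to Treatment and follow-up of AEs in Section 8.4.7". Section 8.4.7 says "For the treatment and follow-up of AESIs please refer to Section 8.4.1.3". The Table 2 instructions in 8.4.1.3 say "please also refer to General withdrawal criteria, Section 7.1".

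**The concern.** A finding that the protocol treats as urgent for reporting, and as a possible reason to withdraw the patient, is placed by the table in the tier with the slower repeat and the lighter work-up. A site that classifies the patient from Table 2 gets a different instruction from one that starts at the AESI list.

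Liver safety is a known question for this drug. Section 2.3.1 records raised LFTs in a small number of patients on linaprazan, the active metabolite, although it argues that the lower peak concentration after X842 reduces the risk. Other features make the INR combination harder to dismiss:

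- ALT or AST above 1.5 × ULN at screening is exclusionary (5.2), so a value above 3 × ULN is more than double the highest level allowed at entry.
- Warfarin is prohibited (5.3.2), which removes one common benign explanation for a raised INR.
- There is no data monitoring committee (9.6), so follow-up at the site carries more weight.
- Under 10.1.9, five X842 patients with the same type of AESI, at no less than twice the comparator frequency, stop the study. A patient can count toward that rule while meeting only the lighter tier.

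**Working it through.** The plan gives no figure to reproduce. The check applies the three sets of rules to the same patient, then compares the testing that each row requires.

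**Classification.** Each profile has normal TBL and ALP and nothing beyond what is shown.

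| Profile | Table 2 | AESI | Section 7.1 |
|---|---|---|---|
| ALT 4 × ULN, INR 1.6 | A | yes, item c | yes |
| ALT 5.0 × ULN, INR 1.6 | A | yes, item c | yes |
| ALT 6 × ULN, INR 1.6 | B (ALT above 5) | yes, item c | yes |
| ALT 4 × ULN, INR 1.6, but TBL 2.5 × ULN | B (TBL above 2) | yes, item c | yes |
| ALT 3.0 × ULN, INR 1.6 | none | yes, item c | no |

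The first two rows are the gap. The next two show its limits: a further row B criterion moves the patient to row B. The last row is a boundary effect, because the AESI item uses at least 3 × ULN while Table 2 and 7.1 use above 3 × ULN.

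**Time to the next scheduled laboratory.** Safety laboratories fall at Visit 3 (Day 7 ± 2) and Visit 5 (Day 28 −2/+5), from the Schedule of Assessments.

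- Nominal gap: 28 − 7 = 21 days.
- Shortest gap: (28 − 2) − (7 + 2) = 17 days.
- Longest gap: (28 + 5) − (7 − 2) = 28 days.

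**Testing required after an abnormality on Day 7.** Row A fixes one repeat within 7 days and then sets no frequency. Row B requires at least 2 tests per week until values settle, so the minimum over d days is 2 × d / 7.

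| Days until values settle (assumed) | Row B minimum tests |
|---|---|
| 7 | 2.0 |
| 14 | 4.0 |
| 17 | 4.9 |
| 21 | 6.0 |
| 28 | 8.0 |

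Time to settling is an assumption, as is continued follow-up of the patient; the documents give neither.

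**The case against.** The strongest reply is that Table 2 should not be read alone. Section 8.4.1.3 also says that PDILI events call for prompt action, testing and monitoring, with Medical Monitor notice within 24 hours, early discussion of the patient and an assessment of whether to stop the drug. A liver AESI with raised INR is hard to see as falling outside that. Row B has a catch-all for adverse events that may point to liver toxicity, and clinically significant laboratory values can be adverse events (8.4.1.1). Section 8.4.3.1 requires a causality rating for every adverse event, and 8.4.7 has its own rule for following events until resolution or the end of the study. One week is also an upper limit, not a target.

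Most of this stands, and it rules out a stronger reading. A reader might infer that the protocol lets such a patient go a week untested with no causality assessment. The documents do not support that: the PDILI duty points to earlier testing, and a causality rating is always required. What row A lacks is the fuller work-up by exclusion of other causes.

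The reply does not settle the classification. PDILI has no threshold. The catch-all's footnote lists liver conditions and neoplasms and does not name INR, so that route depends on judgement. If the PDILI duty does apply, its call for immediate testing conflicts with a repeat allowed at any time within a week.

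A reader might also infer that three further findings with ALT or AST above 3 × ULN are wrongly placed. Section 7.1 accepts "right upper quadrant pain or tenderness, fever, rash, and/or eosinophilia" singly (eosinophilia above 5%), while row B needs rash together with eosinophilia and does not list fever. This is a defensible choice in favour of specificity. These signs often have other causes, fever and rash are AESIs only when believed related to hepatitis or hypersensitivity, and isolated eosinophilia is not named as an AESI.

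**Conclusion.** The gap holds for one combination: ALT or AST above 3 and up to 5 × ULN, INR above 1.5, TBL no more than 2 × ULN, and no other row B criterion. By the table's terms this is row A, although the protocol elsewhere treats it as an unconditional AESI and a severe laboratory abnormality. The surrounding text makes the practical consequence smaller than the table alone suggests, but leaves sites with conflicting instructions.

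The difference in stated testing is one fixed repeat against about 2 to 6 tests over the nominal gap, or up to about 8 with the widest visit windows, depending on when values settle. The documents do not say how often the combination occurs, so no patient count is claimed. The Medical Monitoring Plan and Safety Management Plan (10.2.3) are not among the documents and may add rules.

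**What to change.** Add one criterion to the laboratory events in Table 2, row B: ALT or AST > 3 × ULN and INR > 1.5. Use it in this protocol's wording and in any successor protocol. INR is already in the safety panel (8.3.5), so no new type of test is needed. The cost is a line of text and a few extra blood tests in affected patients.

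This study is already unblinded (SAP amendment, Section 3), so the wording cannot change the follow-up its patients received. An optional listing could show, by arm, patients with ALT or AST above 3 × ULN and INR above 1.5 and the follow-up done. SAP 4.11.2 already plans an AESI listing, and the adverse event listing in 4.11.1 gives causality, action and outcome. However, the laboratory listings in 4.11.4 put chemistry and coagulation in separate outputs and flag each value on its own. The extra listing would use data already collected.

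Aligning fever, isolated rash and isolated eosinophilia with Section 7.1 is optional and a matter of clinical judgement.

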8.4.1.4 Serious adverse drug reaction

The term serious adverse drug reaction (SADR) is to be used whenever either the Investigator or Sponsor or designee assessed the SAE as possibly or probably related to the IMP.

8.4.1.5 Suspected unexpected serious adverse reaction

A SUSAR is any SADR whose nature or intensity is not consistent with the current version of the IB (unexpected).

8.4.2 Time Period and Frequency for Collecting AE and SAE Information

Collection of AEs will start directly after the ICF has been signed. During the screening period, only AEs related to study procedure will be reported. All AEs (including SAEs) will be collected until the End of Study/Early Termination visit. Any AE with start date on the day or after the IMP administration must be recorded with start time. At the follow-up visit, information on new AEs or SAEs, if any, and stop dates for AEs recorded and ongoing during the dosing period must be recorded. Medical occurrences that begin before the start of study drug but after obtaining informed consent will be recorded in the Medical History Log of the eCRF, not in the AE Log.

Investigators are not obligated to actively seek new AE or SAE after conclusion of the study participation (for follow-up of AEs please refer to Section 8.4.7). However, if the Investigator learns of any SAE, including a death, at any time after a patient has been discharged from the study, and he/she considers the event to be reasonably related to the study drug or study participation, the Investigator must promptly notify the Sponsor or Designee.

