4.4 End of Study Definition

All patients who participate in this study and complete Visit 9 (End of Study/Early Termination) visit are considered to have completed the study (Table 1).

The end of the study is defined as the date of the last visit of the last patient in the study.

5 Study Population

Prospective approval of protocol deviations to eligibility criteria, also known as protocol waivers or exemptions, are not permitted.

The patients possibly eligible will be identified as the follows:

1. Patients identified during their routine endoscopy:
 - Patients must have erosive esophagitis identified during the routine endoscopy, before being considered for study screening (prior to signing the ICF).
 - This routine endoscopy will also serve as the index endoscopy in the study and the report should contain the endoscopy findings using the Los Angeles (LA) classification.
 - This routine endoscopy must be obtained within 7 working days of planned randomization, please refer to [Inclusion criterion #4](#).
2. Patients invited for screening upper endoscopy based on their past medical history (both criteria must be met):
 - a) LA grade C or D disease within the past 5 years before screening, demonstrated with endoscopy (endoscopy report issued by a gastroenterologist/endoscopist is accepted)
 - b) In the Investigator's judgement the patient presents clear symptom relapse: patient may be treated with PPI, discontinued PPI treatment (patient's decision) or is being treatment naïve.

For patients invited for screening upper endoscopy, the ICF will be signed prior to the endoscopy. The screening procedures must start with endoscopy and in case the patient doesn't show LA grade C or D erosions, the rest of the screening procedures must not be conducted. This screening endoscopy must be obtained within 7 working days of planned randomization.

The index/screening endoscopy video/digital image will be anonymized and saved for central storage. Imaging data must meet quality standards for adequate LA grading and must be accompanied by a report and videos/digital images to allow retrospective analysis of the endoscopy findings.

Investigators must keep a record of all screened patients even if they were not subsequently randomized in the study. This information is necessary to verify that patients were selected

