5.4 Screen Failures

Screening failures are defined as patients who consent to participate in the clinical study but are not subsequently randomized/entered into the study. A minimal set of screening failure information is required to ensure transparent reporting of screening failure patients to meet the Consolidated Standards of Reporting Trials (CONSORT) publishing requirements and to respond to queries from regulatory authorities. Minimal information includes demography, screening failure details, eligibility criteria and any SAE.

Patients who do not meet the criteria for participation in this study may be rescreened once. If the re-screening occurs less than 3 months after the first screening visit, serology tests do not need to be repeated.

6 Study Drug

Study drug is defined as any investigational intervention(s), marketed product(s), or placebo intended to be administered to a study patient according to the study protocol.

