8.4.5 Recording Adverse Events

Adverse events must be recorded in the AE Log of the eCRF. The Investigator must provide information on the AE, preferably with a diagnosis or at least with signs and symptoms; start and stop dates, start and stop time; intensity; causal relationship to IMP; action taken, and outcome. If the AE is serious, this must be indicated in the eCRF.

Adverse events, including out-of-range clinically significant clinical safety laboratory values, must be recorded individually, except when considered manifestations of the same medical condition or disease state; in such cases, they must be recorded under a single diagnosis.

If the severity/intensity of an AE increases a new AE Form must be completed in the eCRF.

Adverse events must be documented in clear, unambiguous medical language, without use of abbreviations or acronyms.

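### Protocol 8.4.2 both reports procedure-related screening events as AEs and bars them from the AE Log, and the route for other screening SAEs is unclear

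*Protocol*

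**What the plan says.** The first paragraph of Protocol 8.4.2 opens with "Collection of AEs will start directly after the ICF has been signed" and continues with "During the screening period, only AEs related to study procedure will be reported". It closes with a different instruction: medical occurrences that begin before study drug but "after obtaining informed consent will be recorded in the Medical History Log of the eCRF, not in the AE Log". The closing sentence has no exception for events caused by a study procedure or for serious events.

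Other sections that govern the same window:

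- Protocol 8.4.1.1 and SAP 4.11.1: "Only AEs related to study procedure will be collected between screening visit and the first IMP administration". Footnote 12 of the Schedule of Assessments gives the same scope.
- Protocol 8.4.5: "Adverse events must be recorded in the AE Log of the eCRF".
- Protocol 8.4.4: as a general rule, abnormal findings at screening belong in Medical History.
- Protocol 8.4.6: every SAE and AESI is reported within 24 hours of knowledge. No exemption for screening is stated.
- Protocol 5.4, on screen failures: "Minimal information includes demography, screening failure details, eligibility criteria and any SAE".
- Protocol Section 5 (Study Population), second recruitment route: "For patients invited for screening upper endoscopy, the ICF will be signed prior to the endoscopy". Screening begins with that endoscopy, and a patient without LA grade C or D goes no further.

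**The concern.** The only AEs that the protocol sets out to collect before dosing are those caused by a study procedure. Read literally, the closing sentence of 8.4.2 keeps exactly those events out of the AE Log. A site that sees a bleed after a post-consent screening endoscopy is told in one paragraph both to report it as an AE and to keep it out of the place where AEs are recorded.

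Two things are at stake. First, filing may differ between sites according to which sentence each one follows. A misfiled complication would appear among pre-existing conditions and be missing from the AE data. Second, a serious event in screening that no procedure caused has no clear route, because the SAE sections ask for it while the AE scope for screening leaves it out.

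**Working it through.** No arithmetic applies: the point depends on no sample size, rate or error level, and the plan states no figure to reproduce. The check sets the instructions side by side and then applies them to each type of event.

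**Instructions for the period from consent to first dose**

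| Place | Instruction |
|---|---|
| Protocol 8.4.2, opening | AE collection runs from consent; procedure-related AEs are reported |
| Schedule of Assessments, footnote 12 | Same |
| Protocol 8.4.1.1 | Procedure-related AEs are collected before first dose |
| SAP 4.11.1 | Same as 8.4.1.1 |
| Protocol 8.4.5 | AEs go in the AE Log |
| Protocol 8.4.2, closing | "Medical occurrences that begin before the start of study drug but after obtaining informed consent will be recorded in the Medical History Log", and not the AE Log |
| Protocol 8.4.4 | Abnormal screening findings go to Medical History, in general |
| Protocol 8.4.6 | All SAEs are reported within 24 hours |
| Protocol 5.4 | Any SAE is part of the minimum data for a screen failure |

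**Do the two rules of 8.4.2 cover the same events?** Yes. Protocol 8.4.1.1 defines an AE as a kind of medical occurrence, and the closing sentence of 8.4.2 uses the same noun. A procedure complication after consent is therefore an AE under the opening of 8.4.2 and a medical occurrence under its close.

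**By event type**

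1. *Complication of a post-consent screening procedure.* Four places collect or report it as an AE (8.4.2 opening, footnote 12, 8.4.1.1, SAP 4.11.1), and 8.4.5 sends it to the AE Log. One sentence forbids that. This is a contradiction.
2. *SAE in a screen failure.* Protocol 5.4 asks for it and 8.4.6 requires the report. If no procedure caused it, 8.4.1.1 and 8.4.2 leave it out of the screening AEs.
3. *SAE before first dose, unrelated to a procedure, in a patient later randomised.* 8.4.6 covers all SAEs, but 8.4.1.1 and 8.4.2 restrict screening AEs to procedure-related ones. The route is unclear.
4. *Non-serious occurrence unrelated to a procedure.* Medical History is the consistent destination. There is no problem here.

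**Who is exposed.** Patients found at a routine endoscopy had it before consent, so any complication starting before they signed falls outside the window. Invited patients have the endoscopy after consent. Other screening procedures, such as blood sampling, follow consent in both groups, so exposure is not strictly confined to invited patients, but the endoscopy is the procedure that matters most.

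**Which outputs are touched.** SAP 4.11 bases all safety summaries and analyses on the Safety Set, which SAP 4.5 defines as randomised patients with at least one dose.

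- For dosed patients, SAP 4.11.1 has overview rows for any AE and any SAE, separate from the treatment-emergent rows, and a listing of all AEs that flags the non-treatment-emergent ones. A complication in the AE Log would appear there. One filed as medical history would go to the medical history summaries of SAP 4.7.
- For screen failures, the SAP names no AE output on the Enrolled set. The screen-failure listing in SAP 4.4.1 is a disposition listing, and the AE listing is arranged by treatment group, which a screen failure does not have.

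**The case against.** The strongest case on the other side is that a coherent reading exists: procedure-related events are AEs, every other pre-dose occurrence is medical history, and the closing sentence of 8.4.2 was meant only for the latter. Protocol 8.4.4 points that way, and several other statements would have no effect if the closing sentence were read literally. This is probably what the authors intended. But the sentence does not say so, and a site that files a complication under Medical History is obeying an explicit instruction. It could also be argued that 8.4.1.1 defines an AE in a patient who has been given a product, so that nothing before dosing qualifies. The same section then collects procedure-related AEs before the first dose, so the protocol itself does not hold to that.

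A reader might infer that screening complications and screening SAEs are lost, or that the 24-hour report is never started. The documents do not support that. Protocol 8.4.6 requires both eCRF entry on the AE and/or SAE page and a separate SAE form sent by e-mail or fax, with a telephone back-up and a paper form if the eCRF is unavailable. The AE Log is not the gate to that process, and the closing sentence of 8.4.2 concerns logging, not SAE reporting. Protocol 5.4 asks for SAEs in screen failures separately.

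It is also fair to say that the consequence is limited. Events that begin and end before dosing cannot be treatment-emergent, and the study-level stopping criteria in Protocol 10.1.9 turn on events related to the IMP or in X842-treated patients. The eCRF completion guidelines and the Safety Management Plan, which the protocol mentions but which are not among the documents, may settle the filing question. All of this stands. It limits the size of the point but does not remove the contradiction in the protocol text.

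**Conclusion.** The plan is wrong as written, in a narrow way. For complications of post-consent screening procedures, 8.4.2 gives two instructions that cannot both be followed, and a site that obeys the second misfiles the event as medical history. For screening SAEs unrelated to a procedure, the recording route is unclear.

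What is established is a contradiction and a risk of inconsistent filing, not a loss of events. In dosed patients the affected outputs are the any-AE and any-SAE overview rows and the AE and SAE listings. For screen failures no AE output is planned wherever the event is filed. TEAE tables, the healing endpoint and dose selection are untouched. The number of events cannot be derived, because the documents give neither the number of patients invited for endoscopy nor a complication rate. The conclusion assumes that sites work from the protocol text and that no unseen guideline overrides it.

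**What to change.** Reconcile the passages in Protocol 8.4.2. Limit the closing sentence to occurrences between consent and first dose that are neither related to a study procedure nor serious. State that procedure-related events and all SAEs in that window go to the AE Log and, if serious, follow 8.4.6. Align 8.4.1.1, footnote 12 of the Schedule of Assessments and SAP 4.11.1, so that the screening scope reads as procedure-related AEs plus all SAEs, and carry the rule into the eCRF completion guidelines.

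In SAP 4.11.1, add a listing of pre-treatment procedure-related AEs and SAEs on the Enrolled set. This covers screen failures, and also anyone randomised but never dosed.

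The cost is one rewritten sentence with matching edits, a guideline line, one extra listing and a few more AE entries at screening. No treatment rule or efficacy analysis changes.
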